	Appendix A: Updated text to remove “draft” since final version of CRFs now available.	
	Appendix E: Removed statement that site confirmation was not finalized since now complete, and clarified that a site list would be provided under separate cover.	
	Appendix F: Removed statement that site confirmation was not finalized since now complete, and clarified that an IRB list would be provided under separate cover. Also added statement that information will be updated throughout study and updated listing will be available upon request.	

ADHF	Acute decompensated heart failure
AF	Atrial Fibrillation
AHF	Acute Heart Failure
CEC	Clinical Events Committee
CIP	Clinical Investigational Plan
CRF	Case Report Form
CRT	Cardiac Resynchronization Therapy
ECG	Electrocardiogram
EF	Ejection Fraction
HCU	Healthcare Utilization
HF	Heart Failure
ICD	Implantable Cardioverter-Defibrillator
ICM	Insertable Cardiac Monitor
IPG	Implantable Pulse Generator
NYHA	New York Heart Association
RAMware	Software downloaded onto LINQ™ device
RR	R-wave to R-wave interval
SAE	Serious Adverse Event

3. Introduction

Medtronic, Inc. is sponsoring the Reveal LINQ™ Heart Failure (HF) study, a prospective, non-randomized, multi-center, observational, pre-market clinical study. The purpose of this clinical study is to characterize Reveal LINQ™ derived data from patients with heart failure by assessing the relationship between changes in LINQ™ derived data and other physiologic parameters with subsequent acute decompensated heart failure events (ADHF).

This document is electronically controlled. Printed copies are considered uncontrolled.

Confidential

The study is utilizing the Reveal LINQ™ device with an investigational LINQ™ HF RAMware. [REDACTED]

[REDACTED] Additionally, the device will collect the standard information collected in the market released LINQ™ device such as atrial fibrillation burden, average ventricular rate during atrial fibrillation (AF), night and day heart rate and heart rate variability. The study will also collect information regarding HF related clinical events during the same period.

The data collected via the LINQ HF investigational RAMware will not be provided to sites for the treatment of the subjects. Following insertion of the LINQ™ device and download of the LINQ HF investigational RAMware, subjects will be followed for up to 3 years post-insertion or until official study closure defined as when Medtronic and/or regulatory requirements have been satisfied per the Clinical Investigation Plan and/or by a decision by Medtronic or regulatory authority, whichever occurs first.

This Statistical Analysis Plan has been designed to document, for internal use, the Reveal LINQ HF Study design and the planned analyses to be included in a final report.

4. Study Objectives

The primary objective is to characterize Reveal LINQ™ derived data from patients with heart failure by assessing the relationship between changes in LINQ™ derived data and other physiologic parameters with subsequent ADHF events.

5. Investigation Plan

The LINQ™ HF study is a Non-Significant Risk Investigational Device Exemption (IDE) study. The study is utilizing the Reveal LINQ™ device with an investigational LINQ™ HF RAMware download. The LINQ™ HF RAMware enables [REDACTED]

[REDACTED]

The single-arm observational study is expected to be conducted at up to 30 centers in the United States. Up to 300 subjects will be enrolled to achieve approximately 40 ADHF events (no more than two per subject will contribute to the cumulative total). Study subjects will be followed for up to 3 years post-insertion or until official study closure defined as when Medtronic and/or regulatory requirements have been satisfied per the Clinical Investigation Plan and/or by a decision by Medtronic or regulatory authority, whichever occurs first. The expected study duration is approximately 4 years representing 1.5 years of enrollments and 2.5 years of follow-up.

This document is electronically controlled. Printed copies are considered uncontrolled.

Confidential

The subject population for the LINQ™ HF study is patients with heart failure with a New York Heart Association (NYHA) Class III. Inclusion and Exclusion criteria are listed below.

INCLUSION CRITERIA

- Patient is 18 years of age or older
- Patient (or patient's legally authorized representative) is willing and able to provide written informed consent
- Patient is willing and able to comply with the protocol, including follow-up visits and Carelink transmissions.
- Patient is NYHA Class III
- Patient had a HF event (HF event defined as meeting any one of the following three criteria):
 1. Admission with primary diagnosis of HF within the last **6 months**, OR
 2. Intravenous HF therapy (e.g. IV diuretics/vasodilators) or ultrafiltration at any one of the following settings within the last **6 months**:
 - Admission with secondary/tertiary diagnosis of HF
 - Emergency Department
 - Ambulance
 - Observation Unit
 - Urgent Care
 - HF/Cardiology Clinic
 - Patient's Home, OR
 3. Patient had the following within the last **3 months**: EF > 50%, then BNP > 200 ng/L or NTpro-BNP > 400 ng/L OR If EF is <50%, then BNP > 400 ng/L or NTpro-BNP > 800 ng/L

EXCLUSION CRITERIA

- Patient is pregnant (all females of child-bearing potential must have a negative pregnancy test within 1 week of enrollment)
- Patient is enrolled in another study that could confound the results of this study, without documented pre-approval from a Medtronic study manager
- Patient has severe valvular heart disease as defined by hemodynamically significant valve stenosis and/or prosthetic heart valve
- Patient has existing IPG, ICD, CRT-D or CRT-P device
- Patient has severe renal impairment (eGFR <25mL/min)

Subjects will have in-office visits at 1 month post-insertion, as well as 6 and 12 months post-insertion. These in-office visits will include NYHA assessment, 6 minute hall walk, [REDACTED], [REDACTED], physical exam, medication assessment, and collection of symptoms and temperature. Blood tests will be performed at the 6 and 12 month visits. Following the 12 month visit, there will be no further required in-office visit until the exit visit in which the RAMware is removed from the device. In addition to in-office visits, subjects will perform monthly manual CareLink transmissions. [REDACTED]

This document is electronically controlled. Printed copies are considered uncontrolled.

Confidential

6. Determination of Sample Size

There are no sample size requirements as this is an observational study. However, 40 ADHF events with LINQ device data available for the most recent 30 days prior to the event will be collected; up to two events per subject may be used in the analysis, and these events must be at least 90 days apart. While any ADHF event with the requisite device data that occurs prior to a subject's exit may be used in the analysis, the sample size was selected in order that data can be derived from an estimated 40 subjects with a ADHF event within 12 months. This provides a conservative estimate of the required number of subjects. The CHAMPION study provides a 12 month KM estimate of HF hospitalization of 30% for Class III subjects¹. To be conservative, it is assumed 25% of enrolled subjects will have at least one ADHF event within 12 months. If the estimate is used as a binomial proportion, a sample size of 300 subjects would accrue ≥ 40 subjects with event within 12 months with $> 99\%$ probability. If the proportion of subjects with ADHF event is lower than 25%, the probability of at least 40 subjects with at least one ADHF event is $> 88\%$ if the underlying proportion of subjects with event is $\geq 16\%$. The projected enrollment number of 300 may be readjusted if the frequency of ADHF events is higher or lower than anticipated.

7. Statistical Methods

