8.7 Enrollment

When a patient and the principal investigator or authorized designee have personally signed and dated the Patient Informed Consent Form, the patient is considered a subject enrolled in the study. The date the subject signed the Patient Informed Consent Form and data protection authorization must be documented in the subject's medical records.

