8.9 Insertion

Within 30 working days of the baseline assessment, the Reveal LINQ™ device will be inserted in the subject. The insertion procedure will be performed in accordance with the Medtronic Reveal LINQ™ implant instructions. After the Reveal LINQ™ device is inserted, the LINQ™ HF investigational RAMware will be downloaded to the device via the 2090 programmer. Use of the recommended implant locations is located in Figure 8 below. Physicians should follow the implant manuals when performing the Reveal LINQ™ implant.

[figure not shown]

Figure 8: Recommended Insertion Locations

The following information is required to be collected at the insertion visit:

- Final system configuration
- Insertion procedure information
- LINQ™ HF Investigational RAMware download
- [REDACTED]
- Device interrogation (media/USB)
- Any Reveal LINQ™ system and procedure-related adverse events
- Any healthcare utilizations
- Any device deficiencies or study deviations

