8.16 Study Exit

A Study Exit eCRF is required for all subjects except in the case of death. Prior to exiting a subject from the study, it is recommended to follow the subject until all ongoing device and/or procedure related AEs are resolved or unresolved with no further actions planned. Following exit, subjects will continue to receive standard medical care. Upon exiting from the study, no further study data will be collected or study visits will occur for the subject. All data available through the time of the subject's exit will be used for analysis.

Subjects are urged to remain in the study as long as possible but may be exited from the study for any of the following situations and will be documented on the Study Exit eCRF:

- Subject did not meet inclusion/exclusion criteria
- Subject was not inserted with a Reveal LINQ™ device
- Reveal LINQ™ removal without re-implantation
- Implant attempted, however no Reveal LINQ™ was implanted
- Subject relocation to another geographic location
- Subject chooses to withdrawal
- Investigator chooses to withdraw a subject
- Subject lost to Follow-Up
- End of battery life of LINQ™ device
- Study Termination

The following information/procedure is to be collected/performed at study exit:

- Reason for exit
- Removal of the LINQ™ HF investigational RAMware from the LINQ™ device
- Medications
- Device interrogation (media/USB)
- Any Reveal LINQ™ system and procedure-related adverse events
- Any healthcare utilizations
- Any device deficiencies or study deviations

In the case that the subject is determined to be lost to follow-up, details of a minimum of two attempts and the method of attempt (e.g., one letter and one phone record or two letters) to contact the subject must be recorded. In addition, follow the regulations set forth by the governing IRB.

If discontinuation is because of safety or lack of effectiveness, the subject shall be asked to be followed for collecting safety data outside the clinical investigation.

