14.2.1 Endpoint Definitions

why is the descriptive statistics redacted? (BN)

The ADHF events as adjudicated by the CEC that will be used in the primary analysis are those that are ≥ 30 days following implant in order to ensure sufficient LINQ™ derived data prior to the event onset are available. A second ADHF event within a subject may be used if the second ADHF event is > 90 days following the first event. In the event a subject has > 2 qualifying ADHF events, only the first two will be used in the primary analysis. Additional analyses including all qualifying ADHF events may be conducted.

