14.2.4 Sample Size

There are no sample size requirements as this is an observational study. The sample size was selected in order that data can be derived from an estimated 40 subjects with a

HF event within 12 months. This provides a conservative estimate of the required number of subjects. The CHAMPION study provides a 12 month KM estimate of HF hospitalization of 30% for Class III subjects.¹⁷ To be conservative, it is assumed 25% of enrolled subjects will have at least one HF event within 12 months. If the estimate is used as a binomial proportion, a sample size of 300 subjects would accrue ≥ 40 subjects with event within 12 months with $> 99\%$ probability. If the proportion of subjects with HF event is lower than 25%, the probability of at least 40 subjects with at least one HF event is $> 91\%$ if the underlying proportion of subjects with event is $\geq 16\%$. The projected enrollment number of 300 may be readjusted if the frequency of HF events is higher or lower than anticipated.

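### The sample-size probability at a 16% event proportion counts any event in 300 enrolled subjects; for events that can enter the analysis, the 12-month figure is about 78% or lower

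*Combined protocol and SAP*

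**What the plan says.** SAP 6 disclaims any formal sample-size requirement but sets a target: "40 ADHF events with LINQ device data available for the most recent 30 days prior to the event will be collected". It says 300 was chosen so that data can be obtained from about 40 subjects with an event within 12 months, and calls this conservative. The planning value is that "it is assumed 25% of enrolled subjects will have at least one ADHF event within 12 months"; protocol 14.2.4 has the same sentence for HF events ("it is assumed 25% of enrolled subjects will have at least one HF event within 12 months"). Used as a binomial proportion, "a sample size of 300 subjects would accrue" at least 40 subjects with an event with >99% probability. At 16% or more the probability is given as >88% in the SAP and >91% in the protocol.

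The conditions on a usable event are set elsewhere:

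- It must be CEC-adjudicated and fall at least 30 days after implant, "in order to ensure sufficient LINQ™ derived data prior to the event onset are available" (protocol 14.2.1; likewise SAP 7.2 and 7.9.2).
- The subject must have received the RAMware download (SAP 7.2).
- Device data must cover at least the 30 days before the event; otherwise the event is dropped and nothing is imputed (SAP 7.4). Protocol 14.4 asks for complete downloads.

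Enrolment comes before insertion. Once the consent form is signed, "the patient is considered a subject enrolled in the study" (protocol 8.7). Insertion follows later: "Within 30 working days of the baseline assessment, the Reveal LINQ™ device will be inserted in the subject" (protocol 8.9). One listed exit reason is "Subject was not inserted with a Reveal LINQ™ device" (protocol 8.16).

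**The concern.** The calculation and the target count different things. The binomial takes all 300 enrolled subjects and any event within 12 months. The target takes only events that pass the timing, RAMware and device-data conditions. Nothing is taken off n for subjects never inserted, or off p for events in the first 30 days or events without data.

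At 25% there is room to absorb such losses. At 16% there is almost none: the expected count is 300 × 0.16 = 48 against a need for 40. The 16% statement is the only probability the plan prints for a low event rate, so a reader will take it as the chance of reaching 40 usable events within 12 months. It is not that chance.

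**Working it through.** **1. The plan's own figures.** Inputs from SAP 6 and protocol 14.2.4: n = 300, at least 40 subjects, p = 0.25 or 0.16. With X ~ Binomial(n, p):

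- P(X ≥ 40 | 300, 0.25) > 0.9999, so >99% reproduces.
- P(X ≥ 40 | 300, 0.16) = 0.912, so the protocol's >91% reproduces.
- P(X ≥ 41 | 300, 0.16) = 0.883, which would explain the SAP's >88% if it was computed for more than 40. As lower bounds, both printed statements are true.

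**2. Slack.** Solving P(X ≥ 40 | 300, p) for p:

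- >91% needs p of at least 15.97%, a loss of (16 − 15.97)/16 ≈ 0.2% of event subjects.
- >88% needs p of at least 15.61%, a loss of about 2.4%.
- 99% needs p of about 18.2%, so the statement at 25% survives a loss of (25 − 18.2)/25 ≈ 27%.

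**3. The 30-day rule alone.** Assume a constant hazard and that any event on days 30 to 365 can qualify:

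p = 1 − (1 − 0.16)^(335/365) = 0.148, expected count 300 × 0.148 = 44.4, P(X ≥ 40) = 0.783.

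If the subject's first event must itself fall on days 30 to 365, p = 0.146 and the probability is 0.752. No loss rate is assumed here, only the shape of the hazard. Entry requires a recent HF event or raised natriuretic peptide, so risk may be front-loaded; the loss would then be larger.

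**4. Adding non-insertion and missing data.** The documents give no rate for either. The values below are assumptions: 5% not inserted gives n = 300 × 0.95 = 285, and p from step 3 (0.1479 at 16%, 0.2321 at 25%) is multiplied by 1 minus the share of events lacking data.

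| Any-event proportion | Events lacking data | Qualifying p | P(X ≥ 40), n = 285, 12 months |
|---|---|---|---|
| 16% | 10% | 0.1331 | 38.5% |
| 16% | 20% | 0.1183 | 14.5% |
| 25% | 10% | 0.2088 | 99.9% |
| 25% | 20% | 0.1856 | 98.2% |
| 25% | 30% | 0.1624 | 86.3% |

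**5. Planned follow-up.** SAP 6 lets any qualifying event before exit count, and SAP 5 plans follow-up of up to 3 years per subject. Take the 16% annual rate, constant hazard, the first 30 days excluded, n = 285, one event per subject, and every subject followed for T months of 30.44 days. Then p = [1 − exp(−h(30.44T − 30))] × (1 − data loss), with h = −ln(0.84)/365.

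| T | 10% lacking data | 20% | 30% |
|---|---|---|---|
| 18 months | 99.5% | 95% | 75% |
| 24 months | >99.9% | >99.9% | 99.6% |

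Second events would add to these figures; deaths and early exits, not modelled here, would reduce them.

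**The case against.** The strongest reply is that the printed sentence is true. It speaks of subjects with at least one event, and for that quantity 91.2% is right. That stands: there is no error of arithmetic.

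The second reply is that SAP 6 does not rely on the 12-month count. It allows any qualifying event up to exit and up to two per subject, and both documents say in their next sentence that the 300 may be readjusted if events are more or less frequent than expected. This also stands. A reader might infer that the study would miss its 40 events at a 16% rate, or that the 16% statement is its only protection against a low rate. Step 5 and the readjustment clause contradict both. One qualification remains: SAP 7.9.4 itself warns that events after 12 months may go unreported because required visits have ended, so the later buffer is somewhat softer than step 5 suggests.

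Third, the 30% source rate is for HF hospitalization, while the study's definition also counts intravenous therapy in several outpatient settings, and the plan had already reduced 30% to 25%. Both work in the plan's favour on the likely event rate. Neither changes what the probability is at a true proportion of 16%.

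Finally, the larger drops in step 4 depend on loss rates that the documents do not supply. That is correct, and they are illustrations only. A reader might infer from them that the 16% threshold should be replaced by something like 20–23%. That range comes only from assuming 5% not inserted and 10–20% of events lacking data, so the documents do not support it as a threshold.

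**Conclusion.** The concern holds in a limited form. The >88% and >91% statements are right for any event in 300 subjects, but they do not describe the events the study needs. For qualifying events within 12 months at a 16% any-event proportion, the plan's 30-day rule alone gives about 78% (75% if only first events count), assuming a constant hazard. Non-insertion and missing data push it lower by an amount the documents do not let anyone fix.

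The >99% statement at 25% should not be grouped with this. It stays at about 98% with an assumed 5% not inserted and 20% of events lacking data, and falls to 86% only at an assumed 30% lacking data.

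The consequence is modest. The study is descriptive, with no hypothesis and no formal sample-size requirement. On the assumptions in step 5, the probability of 40 qualifying events at a 16% annual rate is about 95% or more at 18 months with 5% not inserted and up to 20% of events lacking data. What needs correcting is a stated probability, not the size of the study.

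**What to change.** In SAP 6 and protocol 14.2.4, define n as inserted subjects with the RAMware download and p as the proportion with at least one event that meets the timing and device-data conditions. Then do one of the following, with identical figures in both documents:

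- print the 12-month probability at 16% as about 78% (30-day rule only, constant hazard), or lower with the assumed non-insertion and data-loss rates stated; or
- give the probability over planned follow-up, with the follow-up time and yield assumptions stated (about 95% at 18 months with 5% not inserted and 20% of events lacking data).

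Add one sentence saying that follow-up beyond 12 months, second events and the option to readjust enrolment cover any 12-month shortfall. Leave the >99% statement at 25%, labelled with the quantity it refers to. Do not print 20–23% as a threshold.

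The cost is one paragraph in each document and a less favourable 12-month figure if that option is chosen. No additional subjects, visits or data are needed.

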7.1. Study Subjects

7.1.1. Disposition of Subjects

This is a single-arm study. Subjects who are consented will undergo a planned standard of care surgical procedure. At enrollment, subjects consent to have a Reveal LINQ inserted and investigational LINQ HF RAMware downloaded. Subjects will then return for 1, 6, and 12 month visits and an exit visit. A STROBE diagram will show each of these stages of follow-up through 12 months, with categories for missed visit, death, exit, and early study closure as reasons subjects did not complete a visit. If the study continues beyond 12 months for one or more subjects, there will be a final box with categories for death, exit, and study closure as reasons for study discontinuation beyond 12 months.

7.1.2. Clinical Investigation Plan (CIP) Deviations

Study deviations will result in corresponding Study Deviation eCRFs being completed. These deviations will be summarized with descriptive statistics including, for each type of deviation, how many occurrences there were in the study, and the number of subjects experiencing each type of deviation.

Inclusion/exclusion violations will not result in subjects being excluded from analysis of objectives.

This document is electronically controlled. Printed copies are considered uncontrolled.

Confidential

7.1.3. Analysis Sets

All enrolled subjects who undergo a LINQ insertion and investigational LINQ HF RAMware download will be included in the analysis of the primary objective. Subjects who do not experience ADHF events used in the analysis will still have their data summarized as a reference.

7.2. General Methodology

Data analysis will be performed by a Medtronic statistician or designee, and will be performed once at least 40 ADHF events (as adjudicated by the CEC) occurring at least 30 days post-Reveal LINQ implant have been obtained from subjects who received the downloaded RAMware and have data for the most recent 30 days prior to the event. No more than two events per subject will be included in the analysis, and those two events must be at least 90 days apart.

All analyses will be performed on an "As Treated" basis.

The cohort will include all enrolled subjects who received the downloaded investigational LINQ HF RAMware and experienced ADHF events at least 30 days post-implant. Subjects who do not experience ADHF events may also be included as a reference dataset for baseline readings of measurements (i.e. profile of measurements that do not precede ADHF events).

Any tests of treatment effects will be conducted at a two-sided alpha level of 0.05 unless otherwise stated.

Any change to the data analysis methods described in the protocol will require an amendment only if it changes a principal feature of the protocol. Any other change to the data analysis methods described in the protocol, and the justification for making the change, will be described in the clinical study report.

